Myeloma Urine and Serum Lab tests (SPEP/UPEP/sFLC)	X	CL	Section 5.4.2 Within 28 days of randomization; Central Laboratory analysis; Results must be available prior to first dose of study drug

Table 5.1-1: Screening Procedural Outline (CA209602) - All Subjects

Procedure	Screening Visit	Use of Central (CL) or Local (LL) Lab	Notes
Bone Marrow Aspirate	X	LL	
Section 5.4.2 Bone Marrow aspirate is mandatory. Bone marrow biopsy is optional. Bone marrow biopsy is required if an aspirate sample (at any required time point) is not available due to a dry tap. Plasma cell percentage is required and should be performed locally per institution standard practice, within 35 days of randomization.

	X	CL	
Section 5.4.2 and Table 5.4.2-1 Bone Marrow aspirate is mandatory. Collections are required at screening, \geqVGPR, and every 6 Cycles thereafter until PD. In subjects with confirmed PD, collection is optional upon PD confirmation.

Corrected Calcium	X	LL	
Section 5.4.2; Within 14 days of randomization; Results must be available prior to first dose of study drug.

Skeletal Survey	X	LL	
Section 5.4.3.1 Within 28 days of randomization

CT or MRI assessment for extramedullary soft tissue plasmacytoma	X	LL	
Section 5.4.3.2 Within 28 days of randomization, if subject had a previous extramedullary or bone plasmacytoma

Clinical Drug Supplies			
Randomize	X		First dose of study drug must occur within 5 days of randomization.

Table 5.1-2: Procedural Outline (CA209602) Procedures Cycles 1 & 2 - All Subjects

Procedure	Local Lab (LL) or Central Lab (CL)	Day 1	Day 8*	Day 15	Day 22*	Rest Days 23-28	Notes (within 72 hours prior to dosing) * Day 8 & 22 pertain to the NE-Pd arm only
Safety Assessments							
Targeted Physical Examination		X					Section 5.3.2 Perform prior to dosing, include weight
Vital Signs		X	X	X	X		Section 5.3.2 Temperature, BP, HR. Additional vital signs needed for Cycle 1 for NE-Pd arm as described in section 5.3.2
Performance Status (ECOG)		X					If performed and recorded at screening, to be done on C2D1 only. (Appendix 2)
Serious Adverse Events Assessment		X	X	X	X		Evaluate prior to dosing
Adverse Events Assessment		X	X	X	X		Evaluate prior to dosing
Concomitant Medications		X	X	X	X		Evaluate prior to dosing
Second Primary Malignancy		X					Section 6.7
Laboratory Tests for Safety							*DAY 8 & 22 only pertain to the NE-Pd arm
CBC & Differential	LL	X	X	X	X		Section 5.3.5 Can be drawn up to 3 days prior to dosing

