Serum Chemistry	LL	X					Section 5.3.5 If performed and recorded at screening, to be done on C2D1 only. Can be drawn up to 3 days prior to dosing.

Table 5.1-2: Procedural Outline (CA209602) Procedures Cycles 1 & 2 - All Subjects

Procedure	Local Lab (LL) or Central Lab (CL)	Day 1	Day 8*	Day 15	Day 22*	Rest Days 23-28	Notes (within 72 hours prior to dosing) * Day 8 & 22 pertain to the NE-Pd arm only
Thyroid function test	LL	X*					TSH (reflex to free T3/Total T3 and free T4 if abnormal result) to be performed every *2 cycles (± 7 days) from first dose regardless of dosing schedule (at screening, C2D1, C4D1, C6D1....etc).
Pregnancy Test	LL	X	X	X	X		Section 5.3.5 For WOCBP only. Urine tests must have a sensitivity of at least 25 mIU/mL. Weekly test within 24 hours of study medication
Efficacy Assessments							
Myeloma Urine and Serum Lab tests (SPEP/UPEP/sFLC)	CL	Every 4 weeks from date of first dose of study therapy until confirmed disease progression , regardless of whether subject is on study therapy or subsequent therapy.					Section 5.4.2 Day 1 of each cycle (including Cycle 1) until confirmed disease progression, even if subject is on subsequent therapy. 24- hour urine sample can be collected within ± 7 days of visit, and must be obtained in all subjects
Bone marrow aspirate	LL	See note					Section 5.4.2 Bone Marrow aspirate is mandatory. Bone marrow biopsy is optional. Bone marrow biopsy is required if an aspirate sample (at any required time point) is not available due to a dry tap. Collections are required at screening, \geq VGPR, and every 6 Cycles thereafter until PD. In subjects with confirmed PD, collection is optional upon PD confirmation. Evaluation of percentage of plasma cells and clonality is required and should be performed locally per institution standard practice.
	CL	See note					Section 5.4.2 and Table 5.4.2-1 Collections are required at screening, \geq VGPR, and every 6 Cycles thereafter until PD. In subjects with confirmed PD, collection is optional upon PD confirmation.

Table 5.1-2: Procedural Outline (CA209602) Procedures Cycles 1 & 2 - All Subjects

Procedure	Local Lab (LL) or Central Lab (CL)	Day 1	Day 8*	Day 15	Day 22*	Rest Days 23-28	Notes (within 72 hours prior to dosing) * Day 8 & 22 pertain to the NE-Pd arm only

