Corrected Calcium	LL	Every 4 weeks from date of first dose of study therapy until confirmed disease progression, regardless of whether subject is on study therapy or subsequent therapy.					Serum calcium and albumin from peripheral blood at D1 of each cycle until confirmed disease progression, even if subject is on subsequent therapy
Skeletal Survey	LL	If clinically indicated					See Section 5.4.3.1
CT/MRI Assessment of Extramedullary Soft Tissue plasmacytoma	LL	As clinically indicated					Section 5.4.3.2 (in subjects with baseline plasmacytoma, imaging follow-up should be done regularly per investigator's discretion). Imaging confirmation of disappearance of plasmacytoma is required at time of CR/sCR if it was not confirmed before.
Response Assessment (Per IMWG)		Every 4 weeks from date of first dose of study drug until confirmed progression regardless of whether on study therapy or subsequent therapy.					Section 5.4.1 Response assessments (\geq PR) and PD require confirmation (2 consecutive assessment)s (Appendix 3).

Table 5.1-2: Procedural Outline (CA209602) Procedures Cycles 1 & 2 - All Subjects

Procedure	Local Lab (LL) or Central Lab (CL)	Day 1	Day 8*	Day 15	Day 22*	Rest Days 23-28	Notes (within 72 hours prior to dosing) * Day 8 & 22 pertain to the NE-Pd arm only
Dosing							*DAY 8 & 22 only pertain to the NE-Pd arm
Premedication for Elotuzumab (Elotuzumab Arm Subjects Only)		X	X	X	X		Sections 4.5.1; Nivolumab is infused before elotuzumab in the NE-Pd arm. Elotuzumab premedications can be administered before nivolumab infusion.
Elotuzumab Infusion		X	X	X	X		Section 4.5.1.3 for Elotuzumab window; Nivolumab is infused first on the NE-Pd arm
Nivolumab Infusion		X		X			Section 4.5.1. Nivolumab is infused first on the NE-Pd arm
Pomalidomide Administration		Day 1 - 21 of cycle					Dispense pomalidomide on Day 1 of each cycle per the local risk management program or the Pomalidomide Pregnancy Risk Prevention Plan (Appendix 6).
Dexamethasone Administration		X	X	X	X		Dexamethasone dosing per Section 4.5.1.

Table 5.1-2: Procedural Outline (CA209602) Procedures Cycles 1 & 2 - All Subjects

Procedure	Local Lab (LL) or Central Lab (CL)	Day 1	Day 8*	Day 15	Day 22*	Rest Days 23-28	Notes (within 72 hours prior to dosing) * Day 8 & 22 pertain to the NE-Pd arm only

Table 5.1-3: Procedural Outline (CA209602) Cycles 3 and 4

Procedure	Local Lab (LL) or Central Lab (CL)	Day 1	Day 8	Day 15	Day 22	Rest Days 23-28	Notes (within 72 hours prior to dosing)

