Only data for the procedures and assessments specified in this protocol should be submitted to BMS. Additional procedures and assessments may be performed as part of standard of care; however, the data for these assessments should remain in the subject's medical record and should not be provided to BMS, unless specifically requested from the Sponsor. Safety assessments must be done prior to dosing. The local safety labs (complete blood count, chemistry panel) and procedures may be collected or performed up to 3 days prior to the visit. For subjects who skip a dose, local safety labs results must be collected at least once per cycle.

All subjects will be assessed for safety. Safety evaluations include assessments of AEs, clinical laboratory tests (hematology, chemistry), vital sign measurements, and physical examination with assessment of ECOG PS. Investigators are responsible for monitoring the safety of subjects who have entered this study and for alerting the Sponsor to any event that seems unusual, even if this event may be considered an unanticipated benefit to the subject. The investigator is responsible for appropriate medical care of subjects during the study.

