8.4.3 Safety Analyses

The safety analysis will be performed in all treated subjects. Descriptive statistics of safety will be presented using National Cancer Institute (NCI) Common Terminology Criteria for Adverse Events (CTCAE) version 4.0 by treatment group. Adverse Events (AE), drug-related AEs, Serious Adverse Events (SAE) and drug-related SAEs will be tabulated using worst grade per NCI CTCAE v.4.0 criteria by system organ class and preferred term. On-study lab parameters including hematology, chemistry, liver function and renal function will be summarized using worst grade per NCI CTCAE v.4.0 criteria.

8.4.7 *Other Analyses*

Not applicable

8.5 *Interim Analyses*

Interim Analysis for PFS Futility

At FDA's request on 21-June-2018, a formal PFS interim analysis for futility was conducted in August 2018 based on the database lock on 12-April-2018. The investigator assessed progression events (NPd and Pd arms) were used in this analysis. Prior to running the futility analysis, a futility criteria was defined based on conditional power assuming 85 events (30% information fraction). The stopping criteria for futility was that the conditional power under observed trend is strictly less than 1%. This would correspond to a HR (NPd vs. Pd) boundary of 0.995 and the corresponding conditional power under alternative would be 67.8%, ie if alternative hypothesis is true (HR = 0.667), there is still 67.8% chance that the study will be positive at the final analysis.

Subsequently, after conducting the interim analysis, the decision was made to permanently discontinue enrolment based on insufficient clinical benefit observed at an interim futility analysis for PFS. All futility analyses were conducted by the unblinded independent statistics vendor.

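### Worst-grade hematology in 8.4.3 can look worse for NE-Pd at equal toxicity, because that arm has twice the scheduled blood counts in Cycles 1-2

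*Combined protocol and SAP*

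**What the plan says.** Section 8.4.3 describes safety by treatment group in all treated subjects. For laboratory data it says "On-study lab parameters including hematology, chemistry, liver function and renal function will be summarized using worst grade per NCI CTCAE v.4.0 criteria". It sets no rule restricting the summary to visits that the arms share, makes no adjustment for the number of tests, and carries no caveat about schedule.

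Table 5.1-2 (Cycles 1 and 2) marks the row "CBC & Differential" on Days 1, 8, 15 and 22. The table header says "Day 8 & 22 pertain to the NE-Pd arm only", and the block of safety laboratory tests repeats it: "DAY 8 & 22 only pertain to the NE-Pd arm". The row "Adverse Events Assessment" has the same four marks.

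Serum chemistry is marked on Day 1 only, in every arm, with the note "If performed and recorded at screening, to be done on C2D1 only. Can be drawn up to 3 days prior to dosing". Table 5.3.5-1 places the liver and renal tests in that panel. From Cycle 3 (Tables 5.1-3 and 5.1-4) counts are on Day 1 in all arms.

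Section 5.3 says that results of additional standard-of-care procedures stay in the "medical record and should not be provided to BMS", unless the sponsor specifically asks for them.

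**The concern.** A worst grade is a maximum. For a given course of blood counts, adding measurements can leave the maximum unchanged or raise it, never lower it. If one arm is measured weekly and the others every two weeks, a cytopenia that appears and recovers between two-weekly visits is seen only in the first arm. Setting the arms side by side then mixes a difference in toxicity with a difference in how often anyone looked.

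At stake is the reading of hematologic toxicity for the elotuzumab combination against N-Pd and Pd. Section 8.4.2.3 says NE-Pd data may be analysed several times to support program decisions, so a descriptive table may still carry weight.

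**Working it through.** The plan states no figure for this point, so there is none to reproduce. The check counts scheduled assessments and then asks what the imbalance could do to a worst-grade rate when toxicity is identical.

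**Step 1. Scheduled assessments per arm (Tables 5.1-2 to 5.1-4)**

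| Assessment | Period | NE-Pd | N-Pd, Pd | Ratio |
|---|---|---|---|---|
| Blood count | Cycles 1-2 | 4 + 4 = 8 | 2 + 2 = 4 | 2.0 |
| Blood count, after first dose | Cycles 1-2 | 8 - 1 = 7 | 4 - 1 = 3 | 2.3 |
| Blood count | Cycles 1-4 | 8 + 2 = 10 | 4 + 2 = 6 | 1.67 |
| Chemistry, liver, renal | all cycles | equal | equal | 1.0 |
| AE assessment | Cycles 1-2 | 8 | 4 | 2.0 |
| AE assessment | Cycles 1-4 | 8 + 4 = 12 | 4 + 4 = 8 | 1.5 |

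The Cycle 1 Day 1 count is taken before dosing, which is why 7 versus 3 is the closer comparison for on-treatment toxicity.

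**Step 2. Chance of at least one Grade 3-4 count, equal toxicity**

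Assumptions, none of them in the documents: each count has a 15% chance of being Grade 3-4 in every arm, and counts within a subject share a latent-normal correlation r. With r = 0 the formula is 1 - (1 - p)^k:

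- k = 8: 1 - 0.85^8 = 72.8%
- k = 4: 1 - 0.85^4 = 47.8%

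For r > 0, the independence formula is averaged over the shared subject effect:

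| r | 8 counts | 4 counts | Gap (points) | 7 counts | 3 counts | Gap (points) |
|---|---|---|---|---|---|---|
| 0.3 | 57.5% | 40.7% | 17 | 54.3% | 34.1% | 20 |
| 0.5 | 48.2% | 35.8% | 12 | 45.8% | 30.8% | 15 |
| 0.7 | 38.7% | 30.3% | 8 | 37.1% | 26.9% | 10 |
| 0.9 | 27.2% | 23.3% | 4 | 26.5% | 21.6% | 5 |
| 1 | 15% | 15% | 0 | 15% | 15% | 0 |

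**Step 3. Second model, anchored to rates the protocol quotes**

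Section 1.3.3 gives Grade 3-4 neutropenia of 48% and thrombocytopenia of 22% for pomalidomide with low-dose dexamethasone in an earlier phase 3 trial. They serve here only as anchors for what the two-weekly schedule might show. The threshold is set so that the sparser schedule gives that rate. Correlation decays with time between counts and is expressed per week (simulation of 200,000 subjects). The entries are what the NE-Pd schedule would then show.

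| Sparse schedule shows | Period | Independent | Weekly 0.5 | Weekly 0.9 | Full |
|---|---|---|---|---|---|
| 48% | Cycles 1-2 (7 vs 3) | 78% | 69% | 57% | 48% |
| 22% | Cycles 1-2 (7 vs 3) | 44% | 38% | 29% | 22% |
| 48% | Cycles 1-4 | 69% | 61% | 53% | 48% |

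Both models agree on direction and on the dependence on correlation. The second also shows the excess shrinking once the common schedule from Cycle 3 is included.

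**Step 4. After the fix**

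Restricting Cycles 1-2 to Days 1 and 15 gives 4 versus 4 scheduled counts (3 versus 3 after the first dose). The schedule-driven difference is zero by construction.

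**The case against.** The best opposing arguments are these.

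- **Most safety data are not touched.** This stands. A reader might infer that all the worst-grade laboratory and AE tables are biased against NE-Pd. The documents do not support that. Chemistry, liver and renal tests are scheduled equally. Nonserious events are collected continuously from first dose to 100 days after the last (Section 6.2.1) and may be reported spontaneously (Section 6). Serious events must be reported whenever they occur in the window (Section 6.1.1). A subject seen on Day 15 can still report a Day 8 symptom, so twice the visits is not twice the detection.
- **Off-schedule counts can reach the database.** Partly stands. It would be too strong to say the other arms cannot catch up. The sponsor may request extra results (Section 5.3), clinically significant results go on the AE or SAE form (Section 6.3), and significant worsening on any safety assessment is recorded (Section 6.7). Counts are followed weekly once pomalidomide is interrupted for a severe cytopenia (Section 4.5.5.3). But that follow-up starts only after detection, and AE entries do not fill the laboratory worst-grade table.
- **The Day 8 and 22 note is loose.** Partly stands. It also heads the dosing block, although every arm takes dexamethasone on those days, and it covers the pregnancy-test row, although Appendix 6 asks for weekly tests in the first 28 days. Sites may not have applied it uniformly. As written, however, it limits the counts.
- **More counts can change the course.** Earlier interruption or growth factor could lower later grades. This is possible and could offset some of the excess; the documents give no basis for sizing it.
- **Nothing inferential depends on it.** Stands. The tables are descriptive, and NE-Pd is a closed exploratory arm of 24 subjects. At a 50% rate its 95% interval is about ±1.96 × √(0.25/24) = ±20 points.
- **The SAP may already deal with it.** Section 8.4.2.3 defers NE-Pd details to the SAP, and no separate SAP text with such a rule is in the document reviewed. If one exists, the point is met.

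**Conclusion.** The point holds for worst-grade hematology and, to a lesser extent, for AE terms that rest on blood counts. The schedule imbalance is exact as written: 8 versus 4 counts in Cycles 1-2, 7 versus 3 after the first dose. Section 8.4.3 contains no safeguard against it.

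The size cannot be fixed from the documents. At an assumed 15% per count it is roughly 8 to 17 points for 8 versus 4 counts at correlations of 0.7 to 0.3. It is about 4 points at 0.9 and vanishes at full correlation. It is smaller over the whole on-study period, because schedules match from Cycle 3. These figures assume equal risk on every scheduled day and that sites followed Table 5.1-2 as read here. The 8-versus-4 figures also give the pre-dose count the same 15% risk; removing that count widens the gap slightly.

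A reader might go on to attribute the cross-arm safety figures in Section 1.7 to this imbalance. That is not supported: those figures are deaths and serious adverse events (63% NE-Pd, 58% N-Pd, 50% Pd), which routine count frequency does not plausibly drive. The N-Pd versus Pd contrast has equal schedules and is unaffected. This is a cheap improvement to an exploratory display and does not touch the trial's main conclusions.

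**What to change.** In Section 8.4.3, for any hematology display that sets NE-Pd beside N-Pd or Pd:

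1. Add a worst-grade table that uses only the common scheduled Days 1 and 15 in Cycles 1-2.
2. Keep the all-visit table, with a footnote giving the scheduled counts in Cycles 1-2 (8 for NE-Pd, 4 for each other arm).

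The chemistry, liver and renal tables need no change. Data collection and patient management are not altered. The cost is one extra programmed table. Its drawback is that it ignores some NE-Pd counts, which remain visible in the all-visit table.

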9 STUDY MANAGEMENT

9.1 Compliance

9.1.1 *Compliance with the Protocol and Protocol Revisions*

The study shall be conducted as described in this approved protocol. All revisions to the protocol must be discussed with, and be prepared by, BMS. The investigator should not implement any deviation or change to the protocol without prior review and documented approval/favorable opinion from the IRB/IEC of an amendment, except where necessary to eliminate an immediate hazard(s) to study subjects.

If a deviation or change to a protocol is implemented to eliminate an immediate hazard(s) prior to obtaining IRB/IEC approval/favorable opinion, as soon as possible the deviation or change will be submitted to:

- IRB/IEC for review and approval/favorable opinion
- BMS
- Regulatory Authority(ies), if required by local regulations

Documentation of approval signed by the chairperson or designee of the IRB(s)/IEC(s) must be sent to BMS.

If an amendment substantially alters the study design or increases the potential risk to the subject: (1) the consent form must be revised and submitted to the IRB(s)/IEC(s) for review and approval/favorable opinion; (2) the revised form must be used to obtain consent from subjects currently enrolled in the study if they are affected by the amendment; and (3) the new form must be used to obtain consent from new subjects prior to enrollment.

If the revision is done via an administrative letter, investigators must inform their IRB(s)/IEC(s).

9.1.2 *Monitoring*

BMS representatives will review data centrally to identify potential issues to determine a schedule of on-site visits for targeted review of study records.

Representatives of BMS must be allowed to visit all study site locations periodically to assess the data quality and study integrity. On site they will review study records and directly compare them with source documents, discuss the conduct of the study with the investigator, and verify that the facilities remain acceptable. CRF pages and/or electronic files may serve as the source documents: such as outcome assessments.

In addition, the study may be evaluated by BMS internal auditors and government inspectors who must be allowed access to CRFs, source documents, other study files, and study facilities. BMS audit reports will be kept confidential.

The investigator must notify BMS promptly of any inspections scheduled by regulatory authorities, and promptly forward copies of inspection reports to BMS.

9.1.2.1 *Source Documentation*

The Investigator is responsible for ensuring that the source data are accurate, legible, contemporaneous, original and attributable, whether the data are hand-written on paper or entered electronically. If source data are created (first entered), modified, maintained, archived, retrieved, or transmitted electronically via computerized systems (and/or any other kind of electronic devices) as part of regulated clinical trial activities, such systems must be compliant with all applicable laws and regulations governing use of electronic records and/or electronic signatures. Such systems may include, but are not limited to, electronic medical/health records (EMRs/EHRs), adverse event tracking/reporting, protocol required assessments, and/or drug accountability records).

When paper records from such systems are used in place of electronic format to perform regulated activities, such paper records should be certified copies. A certified copy consists of a copy of original information that has been verified, as indicated by a dated signature, as an exact copy having all of the same attributes and information as the original.

9.1.3 *Investigational Site Training*

Bristol-Myers Squibb will provide quality investigational staff training prior to study initiation. Training topics will include but are not limited to: GCP, AE reporting, study details and procedure, electronic CRFs, study documentation, informed consent, and enrollment of WOCBP.

9.2 *Records*

9.2.1 *Records Retention*

The investigator must retain all study records and source documents for the maximum period required by applicable regulations and guidelines, or institution procedures, or for the period specified by BMS, whichever is longer. The investigator must contact BMS prior to destroying any records associated with the study.

BMS will notify the investigator when the study records are no longer needed.

If the investigator withdraws from the study (eg, relocation, retirement), the records shall be transferred to a mutually agreed upon designee (eg, another investigator, IRB). Notice of such transfer will be given in writing to BMS.

9.2.2 *Study Drug Records*

It is the responsibility of the investigator to ensure that a current disposition record of study drug (inventoried and dispensed) is maintained at the study site for investigational products. Records or logs must comply with applicable regulations and guidelines and should include:

- amount received and placed in storage area
- amount currently in storage area
- label identification number or batch number
- amount dispensed to and returned by each subject, including unique subject identifiers
- amount transferred to another area/site for dispensing or storage
- nonstudy disposition (eg, lost, wasted)

- amount destroyed at study site, if applicable
- amount returned to BMS
- retain samples for bioavailability/bioequivalence, if applicable
- dates and initials of person responsible for Investigational Product dispensing/accountability, as per the Delegation of Authority Form.

BMS will provide forms to facilitate inventory control if the investigational site does not have an established system that meets these requirements.

